#### **2.3.7.8** ANALYSIS OF SECONDARY ENDPOINTS AND ADVERSE EVENTS

Secondary effectiveness endpoints will be compared between groups over time using group differences and 95% confidence intervals for group differences. Adverse events will be summarized by event counts and per subject incidence rates for categories of AE, for specific AEs, by relationship to device and procedure, and for SAEs. Counts will also be summarized by time of onset category and by AE severity. Where applicable, AE summary tables will include 95% confidence intervals for group differences in incidence rates.

For each study group and for important subgroups separately, the primary outcome (i.e., patient success) and secondary endpoints, as well as the incidence of specific complications, will be tabulated and presented by follow-up interval. Comprehensive tables will provide frequency and percentage distributions and descriptive statistics as appropriate in total and for each study group separately. Tables and graphical displays will be provided for both the primary effectiveness and safety populations as appropriate.

Survival analysis methods will be used to describe time to event outcomes including time to secondary surgical intervention.

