#### 2.3.7.2 STUDY SUCCESS

The null hypothesis is that the probability of achieving Month 60 composite clinical success (CCS) for patients implanted with the Simplify Disc device is no more than 0.10 smaller than the probability of ACDF control patients achieving Month 60 CCS. This study will be considered a success if the PS-quintile adjusted, multiple imputation based, 1-sided p-value for rejecting this null hypothesis is less than or equal to 0.05.

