#### 2.3.7.3 DESIGN OF THE OBSERVATIONAL STUDY

One hundred sixty-six (166) subjects were enrolled in the Simplify Disc IDE population. Of these, 16 Simplify Disc subjects were training subjects. The historical ACDF control population included 133 subjects. The 283 available subjects (150 Simplify Disc (excluding training subjects) and 133 historical ACDF control) were assessed via the Propensity Score (PS) sub-classification process. After applying an established heuristic for 3 iterations (6 models), a total of 150 Simplify Disc and 117 historical ACDF control subjects were retained in the final PS designed sample. Analysis of subject demographic and baseline data showed no meaningful differences between the treatment groups. The PS-selected population and PS sub classes defined in the IDE study will be utilized for the purposes of this study. Per the exclusion criteria, additional subjects are not enrolled into the PAS due to reasons that preclude long-term Simplify Disc data collection (e.g., SSI).

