#### 2.3.7.5 SAMPLE SIZE ANALYSIS

For the purposes of sample size calculation, it is estimated that 85% of the estimated 142 Simplify Disc subjects (N=121) who are not terminal failures or lost to follow-up by Month 24 will be available at year 5. It is estimated that 60% of the estimated 106 (N=64) Control subjects who are not terminal failures or lost to follow-up by Month 24 will be available at year 5.

Based on these results, it was conservatively estimated that the 5-year overall success rates would be 70% of the observed rates, that is, 65% and 50% for Simplify Disc and historical ACDF control, respectively. If the success rates in both groups are larger, statistical power will be larger and so this power analysis would be conservative. With sample sizes of 121 and 64, and assuming 65% and 50% success, the power to detect non-inferiority is 96% at a one-sided 0.05 significance level.

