#### 2.3.7.7 ADDRESSING MISSING PRIMARY OUTCOME DATA

Because of the availability of subject level data in controls that correspond to the subject level data to be collected in the prospective study, missing data will be addressed in the same fashion to how missing data would have been addressed in a randomized clinical trial. Multiple imputation will be used to impute missing final NDI in patients otherwise evaluable for primary CCS. For each of 20 imputed data sets, the primary PS stratified device group difference will be made resulting in a standard error for each. The final device group difference will be the average of the multiple imputed datasets and its standard error will account for both within (usual) and between imputation error.

In addition to multiple imputation, sensitivity analysis will be provided based on tipping point analyses. These are analyses in which all possible combinations of successes and failures are assumed for patients missing primary CCS and the fraction of scenarios in which the statistical conclusion changes is summarized. Best case and worst case, all missing success, and all missing failures scenarios will also be summarized.

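### The two-arm secondary endpoints have no stated missing-data method or propensity-score adjustment, although the plan expects about 15% of Simplify and 40% of control subjects to be unavailable at year 5

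*Combined protocol and SAP*

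**What the plan says.** Section 2.3.7.8 gives the method for the secondary effectiveness endpoints in one sentence: "Secondary effectiveness endpoints will be compared between groups over time using group differences and 95% confidence intervals for group differences". It names no imputation, repeated-measures model, weighting or missing-data sensitivity analysis, and it does not mention the PS quintiles that section 2.3.7.2 requires for the primary test. For time-to-event outcomes it adds descriptive survival methods.

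Section 2.3.7.7 deals with missing data and is titled for the primary outcome: "Multiple imputation will be used to impute missing final NDI in patients otherwise evaluable for primary CCS". Its tipping-point and best/worst-case analyses also concern primary composite clinical success (CCS) only.

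Section 2.3.7.5 sets out the expected follow-up. For the device, "it is estimated that 85% of the estimated 142 Simplify Disc subjects (N=121"; for the control, "It is estimated that 60% of the estimated 106 (N=64) Control subjects". Both figures refer to subjects "who are not terminal failures or lost to follow-up by Month 24 will be available at year 5".

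By sections 2.3.6.2 and 2.3.7.8.1, the endpoints with data in both arms are combined neck and arm VAS, motor status, sensory status, treatment satisfaction, disc height and adjacent-level deterioration. SF-12v2, the Dysphagia Handicap Index and the separate neck, left-arm and right-arm VAS are collected for Simplify only.

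**The concern.** The plan forecasts that the control arm will lose a much larger share of its subjects than the device arm between Month 24 and year 5. A by-visit group difference, with nothing further specified, is naturally computed on the subjects seen at that visit. If those who leave differ in outcome from those who stay, each arm's observed rate shifts in proportion to its own loss, and the shifts do not cancel.

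This matters more here than in a randomised trial. Comparability rests on the PS-designed sample, in which "a total of 150 Simplify Disc and 117 historical ACDF control subjects were retained in the final PS designed sample". The roughly 121 and 64 subjects seen at year 5 are no longer that sample, and the secondary section does not say that the quintiles are carried into the comparison.

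Subjects who leave after Month 36 or Month 48 will often have values of the same measures from those visits. Those values carry information about Month 60 that a visit-by-visit comparison does not use. At stake are the Month 60 secondary estimates and the coverage of their 95% confidence intervals.

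**Working it through.** **The plan's own figures.** Retention: 0.85 × 142 = 120.7 (stated 121) and 0.60 × 106 = 63.6 (stated 64). Power, as stated in 2.3.7.5: "With sample sizes of 121 and 64, and assuming 65% and 50% success, the power to detect non-inferiority is 96% at a one-sided 0.05". With the 0.10 margin from 2.3.7.2 and unpooled variance:

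- SE = √(0.65 × 0.35/121 + 0.50 × 0.50/64) = 0.0761
- Power = Φ((0.65 − 0.50 + 0.10)/0.0761 − 1.645) = 95.0%, close to the stated 96%.

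The sample-size section is therefore consistent with itself, and this point does not question it.

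**Unequal loss.** Among subjects in follow-up at Month 24:

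- Simplify: (142 − 121)/142 = 21/142 = 14.8%
- Control: (106 − 64)/106 = 42/106 = 39.6%

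Against the PS-designed sample of 150 and 117 (2.3.7.3), the shares not available are 29/150 = 19.3% and 53/117 = 45.3%. These wider shares include terminal failures before Month 24, so they are not pure dropout, but the imbalance is no smaller on that base.

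**Bias in an observed-case difference.** Let f be the fraction lost, p the rate in all subjects, and d the amount by which the rate in those lost falls below the rate in those retained. Then the observed rate = p + f × d. With the same d in both arms, the bias in Simplify minus control is (0.148 − 0.396) × d = −0.248 × d. The documents give no outcomes for subjects lost, so d is an assumption and is shown as a range:

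| d | Bias (points) | Simulated coverage of nominal 95% CI |
|---|---|---|
| 0 | 0 | 94.6% |
| 0.10 | −2.5 | 93.1% |
| 0.20 | −5.0 | 88.3% |
| 0.30 | −7.5 | 79.9% |

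The coverage figures assume a true common rate of 60%, with 121 and 64 subjects observed. If those lost do better rather than worse, the bias changes sign and favours Simplify. Coverage is then 93.4%, 89.8% and 83.5% for gaps of 10, 20 and 30 points. With no assumption about those lost, the best-to-worst-case range of the group difference is 14.8 + 39.6 = 54.4 points wide.

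**Precision.** Borrowing the 65% and 50% rates for illustration, the 95% half-width is:

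- at 121/64: 1.96 × √(0.2275/121 + 0.25/64) = 14.9 points
- at 142/106: 1.96 × √(0.2275/142 + 0.25/106) = 12.3 points

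The second figure is a ceiling that no analysis of incomplete data reaches. Earlier visits recover part of the gap.

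**The case against.** The strongest reply is that section 2.3.7.8 is silent, not wrong. A reader might infer that the plan prescribes a complete-case comparison. It does not: it names no estimator and no rule for missing values. In the copy reviewed, the text between 2.3.7.8.1 and 2.3.7.11 is also illegible, so a provision there cannot be excluded. Both points stand, and the matter is one of omission. It still needs closing, because an unspecified method leaves the choice open until the data are seen.

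A reader might also infer that the plan corrects for dropout in the primary endpoint and neglects it only here. The documents do not support so sharp a contrast. Section 2.3.7.7 imputes final NDI in subjects who are otherwise evaluable. A subject who has left may have unknown device-failure and reoperation status and so may not qualify. Wholly missing CCS is visibly covered only by the sensitivity analyses. Copying the primary imputation into 2.3.7.8 unchanged could therefore miss the very subjects at issue.

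Third, not all unavailability is ordinary dropout. Under section 2.3.6.2.3, Simplify subjects with secondary index surgery leave the study after their next visit. Imputing their Month 60 pain or motor status as if no surgery had occurred would be a choice of estimand, not a repair of missing data. This stands and shapes the fix.

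Finally, the size of the bias is hypothetical, and even the 20-point gap gives 5 points against a half-width of 14.9. That is fair. Coverage of 88.3% instead of 95% is nevertheless a real cost when the remedy is cheap.

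**Conclusion.** The concern holds for the two-arm secondary effectiveness endpoints: combined VAS, motor, sensory, satisfaction, disc height and adjacent-level deterioration. The expected loss of 14.8% against 39.6% is the plan's own forecast, and no legible section says how it is handled for these endpoints or whether PS quintile enters.

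The bias is about 0.25 × d for a binary endpoint, or 2.5 to 7.5 points for gaps of 10 to 30 points. This assumes an observed-case analysis and the same gap in both arms. The direction is unknown, so nothing supports a reading that the plan favours the device.

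The point does not extend to time-to-event outcomes, where survival methods allow for censoring if it is uninformative. Nor does unequal loss between arms arise for Simplify-only measures. A reader might infer that the trial's conclusion is at risk, but sections 2.3.7.2 and 2.3.7.6 rest non-inferiority and superiority on primary CCS alone. The change is worth making before the Month 60 analysis; it is not a condition of the study's validity.

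**What to change.** Amend section 2.3.7.8 as follows.

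- **Continuous two-arm endpoints (VAS, disc height):** a likelihood-based repeated-measures model using baseline and all available follow-up visits, with arm-by-visit and PS quintile.
- **Binary or ordinal two-arm endpoints (VAS responder, motor, sensory, satisfaction, adjacent-level deterioration):** multiple imputation with earlier values of the same measure, arm and PS quintile as predictors. It should cover subjects missing the whole visit and give PS-stratified differences.
- **Subjects with secondary index surgery:** state separately how they are counted in each endpoint, and do not impute them as if unoperated.
- **Assumption and display:** say that both methods assume data missing at random, so they remove only the bias explained by observed values. Show observed-case results alongside.

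If the illegible sections 2.3.7.9 or 2.3.7.10 already contain such a provision, a cross-reference from 2.3.7.8 is enough.

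The cost is SAP wording, modest programming and one more set of tables, with no new subjects or visits. Section 2.3.7.7 confirms subject-level control data, and section 2.3.6.2 schedules Months 36, 48 and 60. The control visit schedule before Month 36 is not given, so the models should use whatever earlier visits exist in each arm.

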# 2.3.3 STUDY DESCRIPTION

This is a prospective, multi-center post-approval study (PAS) evaluating subjects in the nonrandomized Simplify Disc IDE study compared to ACDF subjects in a non-concurrent historical control Kineflex®|C Disc study. The historical control population will only include the subjects who were selected using a PS model developed in the Simplify Disc IDE study and reviewed by FDA in the approved PMA to establish comparability between the study populations.

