#### 2.3.6.2.3 Study Completion, Termination or Loss to Follow-up

Simpliy Disc subjects are expected to remain in the study until the 60 months post implantation assessment. The study completion/ termination evaluation will be made at the 60 months assessment, or at earlier time point if the subject withdraws or is withdrawn from the study.

Subjects may be withdrawn from a clinical study early due to withdrawal of Informed Consent, loss to follow-up, or Investigator medical decision. Any premature termination from the study will be documented, including the primary reason for withdrawal. In the event of a secondary index surgery requiring removal of a spinal system, every effort will be made to retrieve the explanted device for analysis. The instructions for the surgical technique for device removal of the Simplify Disc are included in the Study Manuals. Any subjects with a device removal of the Simplify Disc or who have any other secondary index surgery will be discontinued from the study after the next follow-up study visit.

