# 2.3.8 SAFETY ASSESSMENT

#### 2.3.8.1 Adverse Events

An adverse event is defined as any clinically significant undesirable clinical occurrence in a subject. Adverse events, whether or not device related, must be reported on the appropriate case report form. Adverse events will be classified based on seriousness, relationship to device and procedure, and severity by the study investigator. Any adverse event that occurred prior to treatment with the medical device will be documented in the patient's pre-operative medical history in the Simplify Disc study. Only adverse events which occurred in the Month 36 through Month 60 visits or are continuing from Simplify Disc IDE study or are new or have worsened during the course of this study will be evaluated in the safety assessment.

Analysis of adverse events will be conducted using the methods specified in section 2.3.7.8.

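### The adverse-event contrasts in Section 2.3.7.8 use per-subject incidence with no visible exposure adjustment, although year-5 availability is assumed to be 85% versus 60%

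*Combined protocol and SAP*

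**What the plan says.** Section 2.3.7.8 summarises AEs by event counts and per-subject incidence, then adds a comparison: "Where applicable, AE summary tables will include 95% confidence intervals for group differences in incidence rates". Section 2.3.8.1 refers AE analysis back to 2.3.7.8 and adds no method.

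Other text that bears on the point:

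- **AE window (2.3.8.1).** "Only adverse events which occurred in the Month 36 through Month 60 visits or are continuing from Simplify Disc IDE study", together with new or worsened events, are evaluated. The visible text does not state the matching start of risk for the ACDF controls.
- **Availability (2.3.7.5).** The section assumes 85% of 142 Simplify Disc subjects (121) at year 5. For controls: "It is estimated that 60% of the estimated 106 (N=64) Control subjects". Both percentages apply to subjects who were neither terminal failures nor lost by Month 24.
- **Partial safeguards (2.3.7.8).** Counts are given by onset time, complications are tabulated by follow-up interval, and a safety population is named. In addition, "Survival analysis methods will be used to describe time to event outcomes including time to secondary surgical intervention".
- **Secondary endpoints (2.3.7.8).** "Secondary effectiveness endpoints will be compared between groups over time using group differences and 95% confidence intervals for group differences".
- **Propensity score.** "The historical control population will only include the subjects who were selected using a PS model developed in the Simplify Disc IDE study" (2.3.3). Section 2.3.7.3 says that the PS population and subclasses from the IDE study will be used here. A PS-adjusted estimator is visibly named only for composite clinical success (2.3.7.2, 2.3.7.6, 2.3.7.7).

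**The concern.** A per-subject percentage treats a subject followed for one year like a subject followed for three. If one group is followed for less time, its crude percentage tends to fall for reasons unrelated to risk. The plan itself expects fewer controls at year 5, and the objective in 2.3.1 is comparative 5-year safety and effectiveness. The intervals in 2.3.7.8 will therefore be read as comparative evidence, even though no decision rule rests on them.

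The denominator matters as much as the loss. The visible text does not say whether the rates are divided by all enrolled subjects, by those at risk in an interval, or by those present at year 5. That choice can change the sign of the difference, so it should be fixed before the data are tabulated.

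A smaller point concerns the PS. The controls are non-concurrent, and the visible text does not say whether the AE and secondary contrasts are stratified on the PS subclasses.

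**Working it through.** **Inputs from the documents (2.3.7.5).** 0.85 × 142 = 120.7, stated as 121. 0.60 × 106 = 63.6, stated as 64. The section's power also reproduces closely: with 65% versus 50%, margin 0.10 and one-sided 0.05, normal-approximation methods give 95.0% to 95.3% against the stated 96%. That figure concerns the primary test and is not affected by this point.

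**Assumed inputs.** The documents give no AE rates or loss pattern. I assume equal true risk *p* in both groups, a constant hazard, and losses *L* of 0.15 (Simplify) and 0.40 (ACDF) over Months 24 to 60.

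**Exposure.** With linear loss, mean follow-up over the 3 years is 3 × (1 + 0.85)/2 = 2.78 years versus 3 × (1 + 0.60)/2 = 2.40 years. Control exposure per subject is about 14% lower.

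**Crude incidence with denominators 142 and 106.** Observed = (1 − L)p + Lm, where m is the share of leavers who had an AE before leaving. With even losses, m = 1 − p/(−ln(1 − p)). At p = 0.30, m = 1 − 0.30/0.357 = 0.159.

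- Simplify: 0.85 × 0.30 + 0.15 × 0.159 = 27.9%
- ACDF: 0.60 × 0.30 + 0.40 × 0.159 = 24.4%
- SE = √(0.279 × 0.721/142 + 0.244 × 0.756/106) = 5.6 points, so the spurious 3.5 points is 0.63 SE.

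| Scenario (p = 0.30) | m | Simplify | ACDF | Ratio ACDF/Simplify |
|---|---|---|---|---|
| All losses just after Month 24 | 0 | 25.5% | 18.0% | 0.71 |
| Month 36-60 window, even losses over 24-60 | 0.106 | 27.1% | 22.2% | 0.82 |
| Even losses, Months 24-60 | 0.159 | 27.9% | 24.4% | 0.87 |
| All losses just after Month 48 | 0.212 | 28.7% | 26.5% | 0.92 |
| All losses at Month 60, or 30% of leavers had an AE first | 0.30 | 30.0% | 30.0% | 1.00 |
| 40% of leavers had an AE first | 0.40 | 31.5% | 34.0% | 1.08 |

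**Continuing AEs.** These exist at entry and are not lost to later dropout. Suppose half of the 30% is continuing (assumed). The other 85% of subjects then have incident risk 0.15/0.85 = 0.176, and m = 0.091.

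- Simplify: 0.15 + 0.85 × (0.85 × 0.176 + 0.15 × 0.091) = 28.9%
- ACDF: 0.15 + 0.85 × (0.60 × 0.176 + 0.40 × 0.091) = 27.1%

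The spurious gap falls from 3.5 to 1.8 points.

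**Denominator.** Take hazard h = 0.10 per year (true 3-year risk 25.9%) and exponential loss with θ = −ln(0.85)/3 = 0.054 and −ln(0.60)/3 = 0.170. Crude incidence is h/(h + θ) × (1 − exp(−3(h + θ))).

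- Divided by 142 and 106: 24.0% versus 20.6%. A nominal 95% interval excludes zero about 10% of the time under equal risk.
- Same events divided by 121 and 64: 0.240 × 142/121 = 28.2% versus 0.2055 × 106/64 = 34.0%. The sign reverses.
- Events and denominators both limited to year-5 subjects: 25.9% in each group, but only if loss is independent of risk.

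**Person-time check (p = 0.30, even losses).** Expected first events are 39.6 over 333 person-years at risk versus 25.8 over 217. Both give 11.9 per 100 person-years, so the artefact disappears under these assumptions.

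**The case against.** The case for leaving the text as it is has several sound parts.

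- **Follow-up time is not ignored.** Interval tables and survival methods are planned, and the list of time-to-event outcomes is open-ended. This stands as mitigation, but neither provision governs the AE incidence differences to which the 95% intervals attach.
- **A population is named, and text is unreadable.** A reader might infer that the plan has no denominator at all. The documents do not support that: a safety population is named, and its definition could sit in the unreadable part around 2.3.7.9-2.3.7.10. What stands is that the visible text does not tie it to the AE rates.
- **85% and 60% are sample-size assumptions.** They describe availability at one visit, not observed retention or the end of AE recording. The percentages above are therefore illustrations.
- **A reader might infer a known bias against one device.** The documents do not support a direction. It depends on the denominator and on why subjects leave. For Simplify Disc some departures are event-related by design, since subjects with a device removal or "who have any other secondary index surgery will be discontinued from the study after the next follow-up study visit".
- **A reader might infer that secondary and AE comparisons ignore the PS.** That reads too much into silence. Controls are limited to the PS-selected sample, 2.3.7.3 carries the subclasses into this study without limiting them to the primary endpoint, and it reports: "Analysis of subject demographic and baseline data showed no meaningful differences between the treatment groups". That statement describes the 150/117 design sample, of which the assumed year-5 numbers are 121/150 = 81% and 64/117 = 55%. A clarifying sentence is still worthwhile, but residual confounding cannot be quantified from the documents.

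**Conclusion.** The point holds as a cheap improvement of low to moderate priority. As visible, 2.3.7.8 specifies a between-group AE contrast that can show a difference when true risk is equal, because follow-up is expected to be unequal and the denominator is not fixed.

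Under even, independent loss the artefact is under one standard error: 0.63 SE for Months 24-60 and 0.88 SE for a Month 36-60 window. It is smaller when many AEs are continuing, zero in some patterns of loss, and of either sign across denominators and causes of loss. All of this rests on assumed AE risks, assumed loss patterns and the sample-size availability figures.

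A reader might infer that the trial's success criteria are compromised. They are not: non-inferiority and superiority are judged on composite clinical success with a PS-adjusted, multiple-imputation analysis, and the AE and secondary intervals carry no decision rule.

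**What to change.** In Section 2.3.7.8:

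1. Make the between-group contrast for new or worsened AEs (any AE, SAE, device- or procedure-related AE) a cumulative-incidence (Kaplan-Meier) or person-year comparison. State the population and the same start and end of time at risk for both groups, consistent with 2.3.8.1.
2. Tabulate AEs continuing from the earlier study separately, as prevalent events.
3. State that the common AE classes, and the secondary endpoints collected in both groups (combined neck-and-arm VAS, motor, sensory, disc height, adjacent-level deterioration, treatment satisfaction), are estimated across the PS subclasses already named in 2.3.7.3, with 95% intervals.
4. Leave AE classes too sparse for stratification unstratified or descriptive.
5. Keep crude counts and per-subject percentages as descriptive tables.

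The cost is extra programming with existing strata and event and visit dates, and slightly wider intervals. At 30% risk with 142 versus 106, the unstratified 95% half-width is 1.96 × √(0.21 × (1/142 + 1/106)) = 11.5 points. With five equal strata it becomes 11.9 points if the Simplify share runs from 40% to 74%, or 12.6 points if it runs from 32% to 82% (both assumed). With 248/5 = 49.6 subjects per stratum and 60% control retention in each, the smallest year-5 stratum would hold 49.6 × 0.26 × 0.60 ≈ 8 or 49.6 × 0.18 × 0.60 ≈ 5 controls, hence item 4. Exposure-based measures remove the artefact of unequal follow-up, but not bias from losses linked to unrecorded AE risk.
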